ambient background sound, identical to the choices in the Mobile Neurofeedback app, which will play in the background of the guided exercises. Participants will be instructed to complete these sessions 4 times a week for 12 weeks.

Unstructured Relaxation (control group): The control group will use a Relaxation app, which is designed to promote relaxation. The Relaxation app, also created by our study team, is aesthetically similar to the Mobile Neurofeedback app and offers the same relaxing background sounds with nature images. To create the most relaxing experience, users can choose a background sound and adjust the volume. Sessions are set for 10 minutes, and participants will be instructed to complete these sessions 4 times a week for 12 weeks.

All participants will be asked to report pain, anger, and stress symptoms before and after each session. All apps include their own logging systems to track usage. Research staff will also directly collect this weekly app usage data from participants' iPods a total of six times (at the two home visits, the two phone calls, and at the 3 and 6-month follow-up visits) during the study period. Devices will be labeled according to FDA requirements for non-significant risk devices. To preserve blinding to study condition, the same label will be used on all devices and will include the most significant side effects possible from any of the interventions.

Risk/Benefit Assessment

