We believe that this study poses minimal risk to participants and that the risk-to-benefit ratio in the proposed study is acceptable. Anticipated risks related to neurofeedback include drowsiness after neurofeedback practice sessions and minor discomfort due to practicing neurofeedback. There is also the chance that participants may experience headaches, dizziness, fatigue, tingling sensations, negative feelings such as anxiety or frustration, or increased risk of seizures among individuals with epilepsy or seizure disorder, although these side effects are rare. To minimize these risks, participants with a history of seizures will be excluded, and all participants will be instructed to practice neurofeedback at a time when they will not need to perform tasks that require high levels of alertness, such as driving or operating machinery. Participants are warned about each side effect prior to enrolling in the study and reminded again during neurofeedback training. Veterans will be asked if they have experienced any side effects during each scheduled study interaction and are instructed to contact research staff if they experience any of these adverse effects in conjunction with using the neurofeedback. Participants are instructed to discontinue use of neurofeedback if any of these adverse effects begins to affect their daily activities.

Mindfulness training or the control relaxation condition do not present a potential for serious risk to the health, safety, or welfare of a subject. It is possible that the process of learning mindful awareness may temporarily increase feelings of discomfort due to increased awareness. Veterans in the mindfulness and relaxing sounds groups will be instructed to discontinue the intervention if they experience any previously unknown adverse effects, to seek medical assistance if they require it, and to report the adverse effects to the researchers.

It is possible that some participants may become upset by interview questions, i.e., in response to

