After accounting for a 3-month attrition rate of 10%, our targeted sample of 300 (100 in each treatment arm) will have 80% power to detect an effect size equivalent to Cohen's $d = 0.42$. This corresponds closely to findings from a published clinical trial of neurofeedback to reduce chronic pain (Jensen et al., 2013), which found 3-month improvements in pain intensity (0-10 rating scale) equivalent to Cohen's $d = 0.38$. Unless otherwise specified, we will fit a mixed longitudinal model with change from baseline to 3 months and 6 months as the response variable, pain stratification group as a blocking factor, randomized treatment as the between-subjects factor, month as a within-subjects factor, the interaction between treatment and month, and baseline score as a covariate. We hypothesize Veterans in the two intervention groups will report less pain at 3 months compared to Veterans in the control group. We also hypothesize Veterans in the two intervention groups will show increased (8–12 Hz) alpha power on EEG at 3 months compared to Veterans in the control group.

Data & Safety Monitoring

Participants will be screened and excluded from study participation if they have epilepsy/seizure disorder. Potential participants will be asked about seizures twice prior to enrollment in the study intervention: once on the phone screen and again during the initial study interview. Participants will be told to discontinue the study intervention if they develop a seizure disorder or have a seizure. Participants will also be asked about seizures at weeks 1, 3, 6, 9, and 12 of study participation, and will be told to stop the intervention if they report one.

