During study participation, participants will be asked about and monitored for all adverse reactions. Individual participants will be told to discontinue their use of the study intervention if they report a moderate or severe adverse determined to be possibly or very likely related to the study. These participants will be instructed to no longer practice the intervention for the duration of their participation, but will be given the opportunity to complete the rest of study data collection visits. Participants will also be routinely asked about suicidal ideation and violent ideation. Participants who report suicidal or homicidal ideation with a plan will be instructed to discontinue their use of the study intervention. We will be reporting every 6 months to an external Data Safety and Monitoring Board (DSMB) independent of the sponsor. The DSMB will monitor subject accrual (including participant withdrawal) and adverse events. They will also provide consultation on safety issues as needed throughout the study.

When a participant expresses suicidal or homicidal ideation, study staff will respond using a standard of practice that has been used successfully in other studies involving military veterans at Duke University (See “Duke specific Psychiatric Emergency SOP” document for the process, and the “Risk Screen Documentation” document for questions used for suicidal and homicidal ideation assessment). The study staff member responsible for the interaction with the participant will be instructed to gather more information from the participant, including information about suicidal plan, means, intent, and history of suicidal behavior. Based on participant’s responses and risk, study staff may respond in a number of ways including offering resources, asking about participant’s linkage to treatment, recommending further evaluation at the ER, initiating involuntary evaluation, or other responses deemed clinically appropriate. If the participant reports ideation over the phone, the participant will be informed that the PI may contact him/her to talk more about his/her thoughts. The study coordinator will obtain current contact information for the participant and inform the PI, who will contact the participant as necessary to ensure participant safety.

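### Do the differing instructions for stopping practice after an adverse event put the comparison between arms at risk?

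*Combined protocol and SAP*

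**What the plan says.** Risk/Benefit Assessment gives two instructions that depend on the arm.

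- **Neurofeedback:** "Participants are instructed to discontinue use of neurofeedback if any of these adverse effects begins to affect their daily activities". The effects meant are those just listed there: drowsiness, minor discomfort, "headaches, dizziness, fatigue, tingling sensations, negative feelings such as anxiety or frustration", and seizure risk in people with a seizure disorder.
- **Mindfulness and relaxation, one shared rule:** "Veterans in the mindfulness and relaxing sounds groups will be instructed to discontinue the intervention if they experience any previously unknown adverse effects". For mindfulness, the section notes that the practice "may temporarily increase feelings of discomfort due to increased awareness". It names no effect for relaxation.

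Data & Safety Monitoring gives an instruction for all arms: stop "if they report a moderate or severe adverse determined to be possibly or very likely related to the study" (the noun after the adjective has dropped out, a clerical slip). The consequence is spelled out: "These participants will be instructed to no longer practice the intervention for the duration of their participation", with the remaining data collection visits still offered. The same section has further all-arm stops, for seizures ("Participants will be told to discontinue the study intervention if they develop a seizure disorder or have a seizure") and for suicidal or homicidal ideation with a plan.

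Study Interventions adds that, to protect blinding, "the same label will be used on all devices and will include the most significant side effects possible from any of the interventions".

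**The concern.** The three triggers test different things: functional impact of a listed effect, novelty, and severity combined with causality. The documents do not rank them or cross-refer between them, and they define neither moderate severity nor what makes an effect previously unknown. Below the all-arm threshold, the same complaint could end practice in one arm and not in another, purely because of how the instruction is worded.

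Practice is the treatment here, so unequal stopping means unequal exposure. Neurofeedback versus control is a hypothesised contrast for both pain and alpha power at 3 months (Purpose of the Study, Aims 1 and 2). Risk/Benefit Assessment also does not say whether its stop is permanent or whether visits continue, while Data & Safety Monitoring answers both questions for its own stop.

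**Working it through.** The plan states no figure on this point, so the check sets the rules side by side and then asks what a difference could do to the analysis.

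**1. Can all the rules be followed at once?** Yes. Each says when to stop, and none says when to continue. A participant stops if any applicable trigger is met, so no event produces conflicting orders.

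**2. Where do the arms differ?**

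| Event | Neurofeedback | Mindfulness, relaxation |
|---|---|---|
| Moderate or severe, judged possibly or very likely related | Stop | Stop |
| Seizure, or ideation with a plan | Stop | Stop |
| Mild, listed, no effect on daily activities | No instruction | No instruction if the effect counts as known |
| Mild, listed, affects daily activities | Stop | No instruction if the effect counts as known |
| Mild, not listed | No instruction | Stop |

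The last row differs however the terms are read, if an effect on no list counts as previously unknown. The fourth row depends on severity being graded separately from daily-activity impact. If interference with daily activities is what makes an event moderate, a related event of that kind already meets the all-arm rule and the difference disappears. Moderate or severe events judged unrelated also fall below the all-arm rule and follow the arm-specific wording.

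**3. What counts as previously unknown?** Risk/Benefit Assessment says that participants are warned of each side effect before they enrol. Design & Procedures puts consent ahead of arm assignment. All arms therefore appear to hear the neurofeedback list, and the common device label points the same way. On that reading the listed effects are known everywhere. Minor discomfort is on that list, so the mention of discomfort for mindfulness alone need not separate mindfulness from relaxation. This is an inference, so it cannot be said flatly that mindfulness versus control is untouched.

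**4. How do the two sections connect?** Risk/Benefit Assessment addresses someone practising at home. It tells neurofeedback users to contact research staff about these effects, and tells the other two arms to report theirs to the researchers. Data & Safety Monitoring takes up events once staff know of them and have judged relatedness. The natural sequence is self-stop, report, staff determination. The documents do not state this sequence, but the reporting clauses support it.

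**5. What would unequal stopping do to the analysis?** Data Analysis & Statistical Considerations compares arms by randomized treatment and gives no rule removing participants who stop practising. Both sections end use of the intervention, not follow-up. Visits stay open after the more serious stop, so there is no reason to close them after a lesser one.

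For scale, take 100 per arm from Design & Procedures: one extra stop is 1/100 = 1 percentage point. As an illustration, suppose that *k* extra neurofeedback participants stop and end with the control arm's mean outcome, while the true difference is the plan's detectable d = 0.42. The contrast becomes 0.42 × (1 − k/100):

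- k = 1: 0.42 × 0.99 = 0.4158, a loss of 0.0042.
- k = 5: 0.42 × 0.95 = 0.399, a loss of 0.021.

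The values of *k* are assumptions; the documents give no event rates. If the extra stops fall in the control arm instead, the shift depends on how much relaxation itself helps, which is not given either.

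**The case for a change.** The strongest case for a change has three parts.

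**Layering does not remove the arm difference.** The self-stop instruction itself differs by arm, and novelty is a different kind of test from functional impact. This stands: a mild unlisted effect brings a stop instruction only outside neurofeedback. But Risk/Benefit Assessment gives a visible reason. It lists specific expected effects for neurofeedback and sees no potential for serious risk in the other two conditions. A functional test for expected effects and a novelty test elsewhere is a defensible response to those risk profiles. Whether one threshold should apply to all arms is a clinical choice for the investigators.

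**Staff have no written basis for deciding on resumption after a self-stop.** The silence on permanence is real. It is partly filled by the reporting clauses, which bring the event to staff, and by the all-arm rule, which tells them when a stop must last.

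**An imbalance could not be explained afterwards, because no field records which trigger applied.** This is true of the trigger. However, all apps log usage, Study Interventions has those data collected six times, and side effects are asked about at each scheduled contact. Unequal practice would therefore be visible by arm alongside the reported events.

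**Conclusion.** The observation is accurate as far as it goes: the stop wording differs by arm for lesser events, and Risk/Benefit Assessment leaves permanence and continued visits unstated. It does not amount to a contradiction, and it does not undermine the primary comparison. The triggers are compatible, the more serious events are treated identically, and arms are compared as randomized with outcome visits still available. Under that comparison, stopping on instruction is part of what each arm was assigned.

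The effect on the estimates cannot be derived. It is probably small, at 1 percentage point of an arm per extra stop, and its direction is not fixed. This rests on three readings: that the pre-enrolment warning reaches all arms, that a self-stop ends practice and not follow-up, and that participants who stop stay in their randomized group. The text supports each without stating it outright. What remains is missing detail that staff can settle sensibly in their working instructions, and no change to the plan follows.
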